### Secondary outcomes

*Other cognitive outcomes.* Cognitive outcomes are assessed such as general cognition, language, verbal memory, visuospatial memory and crystallized and fluid intelligence.

- ि Rey auditory verbal learning test (33). The Total Learning measure (RAVLT-AT) will be the capacity to recall and to accumulate words through the 5 learning trials.
- ि Rey-Osterrieth complex figure (ROCF) (34). The study variables that will be used are: (a) copy—overall sum of correctly drawn elements when copying the model; (b) immediate recall—total sum of correctly drawn items after 3 min.
- ि Boston Naming Test (BNT) (35). The variable that we will use will be the number of correct responses generated requested to the name of each figure.
- ि Wechsler adult intelligence scale IV (36). That tests represent a different cognitive domain: Verbal Comprehension, Working Memory Index, Perceptual Reasoning Index and Processing Speed Index. The variable that we will use will be the number of correct responses generated in each test:
  - Similarities
  - Vocabulary
  - Information
  - Block design
  - Matrix reasoning
  - Visual puzzles
- ि Verbal and semantic fluency test(37). The verbal fluency assessment tests letter fluency (recall as many words beginning with a specific letter) and semantic fluency (recall as many members of a category as possible). The variable that we will use will be the number of words generated by the participant.

*Brain structure and function* (Time frame: Baseline and 24-week). Brain structure and function is assessed by a Siemens Magnetom PRISMA Fit 3T scanner with a 64-channel head coil. Briefly, the following sequences are performed:

- ि T1-weighted Magnetization-Prepared Rapid Acquisition with Gradient Echo (T1-weighted MPRAGE structural): Volume, surface, thickness and shape.
- ि High resolution hippocampus: High resolution Hippocampal subfield segmentation.

- † Resting State Echo-Planar Imaging (EPI): resting state Blood Oxygen Level Dependent (BOLD) fluctuations, activation and functional connectivity.
- † Functional Magnetic Resonance Imaging n-back Task (fMRI n-back task): Task-evoked BOLD fluctuations, activation and functional connectivity.
- † Diffusion weighted acquisition: White matter integrity indicators such as fractional anisotropy, mean diffusivity, radial diffusivity, and axial diffusivity.
- † Three-Dimensional T2 Turbo Spin Echo Fluid Attenuated Inversion Recovery (3D T2 TSE FLAIR): White matter lesions.
- † Pseudo-Continuous Arterial Spin Labeling Turbo Gradient Spin Echo (pCASL TGSE): Blood flow estimates and arterial transit time estimates.

*Brain amyloid beta deposition (Aβ)* (Time frame: Baseline and 24-week). The brain Aβ deposition is assessed using a PET scan Biograph-Vision 600 Edge Positron emission tomography/Computed tomography (PET/CT) digital scanner (Siemens, Erlangen, Germany). [18F]Florbetaben is injected intravenously into each participant in accordance with the applicable regulatory guidelines. PET images are acquired from participants 90 to 110 min after intravenous injection of 300 megabecquerel (MBq)  $\pm$  20% (38). The Standardized Uptake Value Ratio (SUVR) and centiloid values will be used as outcomes.

#### Other outcomes

*Biological samples* (Time frame: Baseline and 24-week). Several biomarkers using blood, saliva, and fecal samples are determined. Blood samples are used to determine traditional blood markers and genotyping and novel blood brain-based biomarkers. In addition, fecal and saliva samples are used to determine microbiome composition and others potential biomarkers.

*Physical Function* (Time frame: Baseline, 12-week and 24-week; gait parameters and 2-km walking test not performed at 12-week). The Senior Fitness Test (SFT) (39) and the Short Physical Performance Battery (SPPB) (40), the 2-km test (only baseline and 24-week) and the Optogait are performed. Briefly, we measure (i) aerobic capacity [i.e., 6-minute walk test (m/6 min) (41), Two-minute step test (n/2 min), Up and Go test (sec) and 2-km walking test (seconds) (42), Chair Sit and Reach Test (cm)], (ii) balance [i.e., Balance test (score of Balance test)], (iii) flexibility [i.e., Chair Sit and Reach test (cm) and the Back Scratch test (cm)] and (iv) gait parameters [i.e., Stride length (cm), Stride time (sec), Step length (cm), Step time (sec)] by the optical Opto Gait system (Microgate Slr; Bolzano, Italy) (43).

*Muscular strength* (Time frame: Baseline, 12-week and 24-week; Gummex Iso-2 dynamometer not performed at 12-week). Measurements are taken to assess both lower and upper muscular strength. Lower body strength was evaluated using the Chair Stand test from SFT (44) and the Gummex Iso-2 dynamometer (EASYTRCH s.r.l., Italy) (45). Upper body strength was assessed through the Arm Curl test from SFT (44), Hand dynamometer (TKK 5101 Grip D, Takey, Tokyo Japan) and the Gummex Iso-2 dynamometer (EASYTRCH s.r.l., Italy) according to the previous published protocol (45).

*Physical activity monitoring* (Time frame: Baseline and 12-week). Movement behaviors are monitored using the Actigraph GT3X + accelerometry device (Pensacola, FL, USA). Participants wear the device on their non-dominant wrist for a continuous span of 9 days, with removal only during activities such as showering. Alongside the device, participants maintained a diary to record in-bed and out-of-bed times, naps, and periods when the device is not in use.

*Anthropometric, body composition and blood pressure measurements* (Time frame: Baseline and 24-week). Body weight (kg) measured in triplicate with an electronic scale (SECA 861, Hamburg, Germany). Height (cm) assess with a precision stadiometer (SECA 225, Hamburg, Germany). Head, neck, waist and hip circumference are measured. Body composition is measure using dual energy X-ray absorptiometry (DXA, Discovery Densitometer from Hologic). A total body scan as well as specific assessment of both hips and lumbar spine are performed to determine body composition and bone density parameters. Validated automated blood pressure monitor (Omron M3, Intellisense) is used to take blood pressure measurements.

*Psychosocial, mental health and other questionnaires.* A battery of questionnaires is administered including the following dimensions: mental health, psychological health, functional ability, medical information, lifestyle behaviors, and others. Exercise self-efficacy, social provisions and groups. mood and anxiety, personality traits, social networks, pain, fatigue, etc. As such, we carefully selected a battery of tests that would considerably extend the knowledge on how exercise influences cognitive and brain health. The time frame of each questionnaire is present in table 2.

Table 2. Time frame of questionnaires

Questionnaire	Baseline	12-week	24-week
Mental health			
Geriatric Depression Scale (GDS)	x		x
Hospital Anxiety and Depression Scale	x	x	x
Perceived Stress Scale (PSS)	x		x
Rosenberg Self-Esteem Scale (RSE)	x		x
Satisfaction With Life Scale (SWLS)	x		x
UCLA Loneliness Scale (UCLA-L)	x		x
Psychological variables			
Social media use	x		x
Social Support Questionnaire	x		x
Big Five Inventory (BFI)	x		x
Short Form 36 Health questionnaire (SF-36)	x	x	x
Functional ability variables			
Instrumental activities of daily living	x		x
International Fitness Scale (IFIS)	x		x
Mobility and agility questionnaire	x	x	x
Questions about energy and frailty	x	x	x
McGill Pain Questionnaire	x	x	x
Medical history			
Health history	x		x
Medication list	x		x
Oral health questionnaire	x		x

COVID questionnaire	x		x
Adverse event report	x		x
Lifestyle behaviors			
Drinks questionnaire	x		x
Food-frequency Questionnaire (FFQ)	x		x
MEDAS-14	x	x	x
Smoking questions	x		x
Sitting time questionnaire	x		x
Physical activity assessment	x		x
Pittsburgh Sleep Quality Index (PSQI)	x		x
Others			
Demographic questions	x		x
Edinburgh Handedness Inventory (EHI)	x		x
Mental health	x		x
Geriatric Depression Scale (GDS)	x		x
Hospital Anxiety and Depression Scale	x		x
Perceived Stress Scale (PSS)	x		x
Rosenberg Self-Esteem Scale (RSE)	x		x
Satisfaction With Life Scale (SWLS)	x		x
UCLA Loneliness Scale (UCLA-L)	x		x
Psychological variables	x		x
Social media use	x		x
Social Support Questionnaire	x		x
Big Five Inventory (BFI)	x		x
Short Form 36 Health questionnaire (SF-36)	x		x
Functional ability variables	x		x

## 5.2 Analysis methods

The main analyses will consist of the intention-to-treat analyses for the primary and secondary outcomes using a constrained linear mixed model (cLMM). The model will include fixed effects for time (three levels or two levels, depending of the outcome) and treatment (two levels) as well as the unique participant identifier as a random effect. Model assumptions will be checked. In case we detect model violations, we will take appropriated measures by, for example, conducting data transformations. The treatment effects will be presented by estimated marginal means and standard errors for changes. The specific differences between analysis are described in the following's points divided into primary analysis, secondary and others outcomes.

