## 2.2 Randomization

Randomization (1:1) occurs on a rolling basis and only after the completion of all baseline assessment sessions by the participant to reduce the risk of bias during the assessment. We use a computerized randomization protocol (stratified by age and sex) through the REDCap Software (22) that incorporate a checklist to make sure all assessments have been completed and the data have been adequately entered into the database.

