### 5.2.1 Primary analysis.

#### Effects on primary outcomes

To investigate the overall effect of the resistance exercise intervention on the change from baseline to post-intervention in the executive function composite score, cLMM approach with repeated measures over time (baseline, 12-week and 24-week outcomes) will be used using an intention-to-treat principle. This statistical linear mixed model will include both a random intercept for each participant and a group-by- time interaction as a fixed effect.

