### 5.2.2. Secondary analyses

#### *Effects on secondary outcomes*

To investigate the effect of the resistance exercise intervention on the secondary outcomes (other cognitive outcomes, brain structure and function and AB), the same analyses as the primary analysis using an intention-to-treat principle and cLMM analysis will be performed. The preprocessing analysis of brain structure and function measured with MRI will be carried out as secondary analyses using different programs (Freesurfer, FSL, CON, fMRIprep).

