#### *Moderators and mediators*

In addition, mediation and moderation analysis will be performed following AGRema (A Guideline for Reporting Mediation Analyses) recommendations (46), using the group as independent variable (intervention group vs control group), executive function as outcome, and mediating and moderating variables.

Moderators include will be sex, age, education, apolipoprotein E (APOE) status, and A $\beta$  status. Additionally, baseline data of various cognitive measures, including the composite executive function score, Trail Making Test, Digit Symbol Substitution Score, Dimensional Change Card Sort Test, and Spatial Working Memory, will be incorporated. The baseline values of strength measures and mental health variables, specifically depression and self-esteem, will be also analyzed. We will also assess the potential mediators, aiming to understand the mechanisms through which the intervention could exert its effects. No interim analysis will be performed.

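### Randomisation is stratified by age and sex, but the primary mixed model fits neither, so its standard error is slightly too large

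*SAP*

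**What the plan says.** Section 2.2 describes the allocation: "We use a computerized randomization protocol (stratified by age and sex) through the REDCap Software". It mentions neither block size nor age bands.

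Section 5.2 gives the general model: "The model will include fixed effects for time (three levels or two levels, depending of the outcome) and treatment (two levels", plus a random effect for participant. Section 5.2.1 says that the primary model has a "random intercept for each participant and a group-by- time interaction as a fixed effect". Neither section contains a term for age or sex.

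Section 5.2.2 carries this model over to the secondary outcomes ("the same analyses as the primary analysis using an intention-to-treat principle and cLMM analysis will be performed") and uses the same formula for the other outcomes. Apart from the allocation and the eligibility age range, age and sex appear only as baseline descriptors in section 4.5 and as effect modifiers in section 5.2.2: "Moderators include will be sex, age, education, apolipoprotein E (APOE) status".

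The standard error is itself a planned result. Section 5.2 states: "The treatment effects will be presented by estimated marginal means and standard errors for changes".

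**The concern.** Stratified allocation forces the arms to be nearly alike in the stratification factors. If those factors predict the outcome, the treatment estimate varies less from one randomisation to the next than under simple randomisation. A model that omits the factors does not know this. It leaves their variance in the participant intercept and residual, and computes a standard error as if chance imbalance in age and sex could still occur.

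The estimate stays unbiased and type I error does not rise. What is lost is calibration and some power: the interval is wider than the design warrants and the test rejects a true null less often than 5%. With 90 participants, precision that costs nothing is worth having.

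**Working it through.** The SAP states no standard error or precision figure for this model, so there is none to reproduce.

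**Inputs from the SAP.** 45 participants per arm, visits at baseline, 12 and 24 weeks (section 2.1); effect size 0.34, two-sided 5% level, 20% dropout (section 2.3).

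**Inputs assumed.**
- ρ: total within-person correlation, equal between all visits, as a random intercept implies.
- R²: share of outcome variance explained by age and sex, constant over time.
- Outcome SD of 1, with 0.34 read as a standardised difference.
- Allocation balanced within age-by-sex strata.

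**Closed form, complete data.** With a common baseline mean, the 24-week effect is estimated by D24 − ρ·D0, where D is the between-arm difference at that visit. The 12-week visit drops out. Let r = (ρ − R²)/(1 − R²) be the correlation left after age and sex are removed. The variance is 2/45 times a factor:

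- reported by the unadjusted model: 1 − ρ²
- true, unadjusted estimate with balanced strata: (1 − R²)(1 + ρ² − 2ρr) = (1 − ρ²) − R²(1 − ρ)²
- adjusted for age and sex: (1 − R²)(1 − r²)

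| ρ | R² | Reported | True | Adjusted | Reported SE over true SE | Unadjusted SE over adjusted SE |
|---|---|---|---|---|---|---|
| 0.5 | 0.1 | 0.750 | 0.725 | 0.722 | +1.7% | +1.9% |
| 0.5 | 0.2 | 0.750 | 0.700 | 0.6875 | +3.5% | +4.5% |
| 0.5 | 0.3 | 0.750 | 0.675 | 0.643 | +5.4% | +8.0% |
| 0.7 | 0.1 | 0.510 | 0.501 | 0.500 | +0.9% | +1.0% |
| 0.7 | 0.2 | 0.510 | 0.492 | 0.4875 | +1.8% | +2.3% |
| 0.7 | 0.3 | 0.510 | 0.483 | 0.471 | +2.8% | +4.0% |
| 0.8 | 0.2 | 0.360 | 0.352 | 0.350 | +1.1% | +1.4% |
| 0.9 | 0.2 | 0.190 | 0.188 | 0.1875 | +0.5% | +0.7% |

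The sixth column is the error in the reported standard error: √(reported/true) − 1. The seventh also includes the small real gain in efficiency from adjustment. For example, at ρ = 0.5 and R² = 0.2 the reported SE is √(2 × 0.75/45) = 0.183, the true SE is √(2 × 0.70/45) = 0.176 and the adjusted SE is √(2 × 0.6875/45) = 0.175.

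**Simulation of the planned model.** Three visits, REML, 90 participants, blocks of 4 within age-by-sex strata with an assumed age cut at 72, 20,000 replicates:

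| R², ρ | Cut in mean SE from adding main effects | Type I error, unadjusted to adjusted | Power at 0.34, unadjusted to adjusted |
|---|---|---|---|
| 0.2, 0.5 | 4.2% | 0.0445 to 0.0510 | 46.3% to 49.8% |
| 0.2, 0.8 | 1.4% | 0.0493 to 0.0516 | 77.1% to 78.0% |
| 0.3, 0.5 | 7.4% | 0.0411 to 0.0524 | not run |

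The Monte Carlo standard error of these type I rates is √(0.05 × 0.95/20,000) = 0.0015. In the first scenario the empirical SD of the estimate fell only from 0.178 to 0.175, so most of the change lies in the reported SE. Adding by-time terms for age and sex gave a cut of 4.1% there instead of 4.2%. The power levels depend on the assumed ρ; only the differences bear on this point.

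With 20% dropout by week 24, half of it by week 12 (3,000 replicates, R² = 0.2), the cut was 4.0%, 2.1% and 0.6% for ρ of 0.5, 0.7 and 0.9.

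A second, independent simulation (2,500 runs per scenario) gave ratios of unadjusted to adjusted SE between 1.010 and 1.080.

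**The case against.** Four points deserve weight.

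*The analysis is valid as written.* It is unbiased and errs on the conservative side. That is true, and it makes this a recommended improvement, not a correction of an invalid analysis.

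*The size rests on unsupported inputs.* The SAP gives neither ρ nor R². A sample limited to ages 65 to 80 and screened as cognitively normal may show little age or sex effect. At R² = 0.1 the unadjusted SE exceeds the adjusted one by only 0.3% to 1.9% for ρ from 0.9 down to 0.5, and if neither factor is prognostic the excess is nil. This stands.

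*Balance within strata is assumed.* Section 2.2 does not mention blocking. In a simulation with unblocked allocation inside strata (R² = 0.3, ρ = 0.5, Monte Carlo error about 0.6 points) the overstatement vanished. But stratifying without any balancing device would balance nothing, so balance within strata is the ordinary reading. It must still be named as an assumption.

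*The larger percentages mix two things.* Unadjusted over adjusted SE, up to 8.0%, includes an efficiency gain. The error in the reported SE is the smaller figure, at most 5.4% in the cases examined. The two should be kept apart.

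**Conclusion.** The point holds. The SAP stratifies by age and sex and leaves both out of the primary model and every model copied from it. Over ρ from 0.5 to 0.8 and R² from 0.05 to 0.30, the reported standard error is 0.3% to 5.4% too large; at ρ = 0.7 it is 0.9% for R² = 0.1 and 1.8% for R² = 0.2. At R² = 0.2, adjustment adds about 3.5 percentage points of power at ρ = 0.5 and 0.9 points at ρ = 0.8.

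These figures assume that age or sex is prognostic, that allocation is balanced within strata, and that visits are equally correlated. Sizes were worked out for a generic standardised outcome, with the primary composite in mind; none was computed for any particular secondary outcome. The consequence is minor and conservative, and removing it is nearly free.

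**What to change.** Add to section 5.2, for example: *The stratification factors, sex and age, are included as fixed effects in the constrained mixed model for the primary outcome and for all outcomes analysed with the same model.* State there whether age enters as continuous years or in the randomisation bands, so that no choice is left for after the data are seen. Main effects are enough. If by-time terms are wanted, say so in advance. The unadjusted model can stay as a supportive analysis. It would also help to state in section 2.2 whether allocation is blocked within strata, and the age bands used.

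The cost is one sentence and two degrees of freedom with continuous age, a few more with bands. Both variables are known for every participant at randomisation.

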### 5.2.1 Primary analysis.

#### Effects on primary outcomes

To investigate the overall effect of the resistance exercise intervention on the change from baseline to post-intervention in the executive function composite score, cLMM approach with repeated measures over time (baseline, 12-week and 24-week outcomes) will be used using an intention-to-treat principle. This statistical linear mixed model will include both a random intercept for each participant and a group-by- time interaction as a fixed effect.

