## 5. Analysis

### 5.1 Outcome definitions

The primary outcome is assessed at baseline (before randomization), at mid-point (12-week) and after the intervention (24-week) while some of secondary outcomes are assessed only at baseline and post intervention (24-week, Table 1).

Table 1. Time frame and specific outcomes of cognitive tests.

Executive function test	Baseline	12-week	24-week	Specific outcome
Trail making test A and B	x	x	x	Interference score
Digit symbol substitution test	x	x	x	Total number of correctly paired symbols
Dimensional card sort task	x		x	Inverse efficiency score
Spatial working memory	x	x	x	Inverse efficiency score
Picture sequence	x		x	Theta score
List sort working memory	x		x	Raw score corrects trials
Flanker	x		x	Incongruent trials inverse efficiency score
Stroop task	x	x	x	Interference score
Task-switching	x	x	x	Global Cost
Other cognitive test	Baseline	12-week	24-week	Specific outcome
Rey auditory verbal learning test	x		x	Total recorded words
Rey-Osterrieth complex figure	x		x	Correct drawn elements
Boston Naming Test	x		x	Correct responses
Wechsler adult intelligence scale IV				
T Similarities				
T Vocabulary	x		x	
T Information				
T Block design				
T Matrix reasoning				
T Visual puzzles				
Verbal and semantic fluency test	x	x	x	Correct responses

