### 5.3 Missing data

The number of missing data will be reported and patterns of missing data will be explored. Based on previous experience, we expect that missing data will be assumed as missing at random. Therefore, the linear mixed model analyses will handle our missing data. However,

once the data processing is finalized, we reconsider this expectation. In case we believe this assumption does not hold, we will explore appropriate measures for the data analyses.

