#### *5.6 Statistical software*

The analyses of the primary outcomes will be performed using R. For the main analyses, we will use the ‘LMMstar’, lmer, nlme and lavaan packages. The use of specific packages will be reported in each manuscript. In addition, specific software’s are used for secondary brain outcomes.

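### The primary model has a participant random intercept and no stated residual covariance, so the 24-week standard error rests on an unsupported compound-symmetry assumption.

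*SAP*

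**What the plan says.** Section 5.2 sets out a constrained linear mixed model with fixed effects for time and treatment, "as well as the unique participant identifier as a random effect". Section 5.2.1 applies it to the primary outcome as a "cLMM approach with repeated measures over time (baseline, 12-week and 24-week outcomes"), aimed at the change from baseline to post-intervention, and adds: "This statistical linear mixed model will include both a random intercept for each participant". Its only other stated term is the group-by-time fixed effect. The word constrained is not explained as a choice of covariance.

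On departures from the model, section 5.2 says: "In case we detect model violations, we will take appropriated measures by, for example, conducting data transformations". Section 5.3 leaves incomplete data to the same model: "Therefore, the linear mixed model analyses will handle our missing data". Section 5.6 lists LMMstar and the "lmer, nlme and lavaan packages" without a covariance option.

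In section 5.1, "Table 1. Time frame and specific outcomes of cognitive tests" marks five of the nine executive tests at 12 weeks: Trail Making, digit symbol, spatial working memory, Stroop and task-switching. Dimensional card sort, picture sequence, list sort and flanker are marked only at baseline and 24 weeks. The primary outcome has three visits, "while some of secondary outcomes are assessed only at baseline and post intervention". Section 5.2.2 carries the primary method over to all secondary and other outcomes.

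**The concern.** A random intercept with independent, equal-variance residuals is compound symmetry: the composite has the same variance at every visit, and the 0–12, 12–24 and 0–24 week correlations are all equal. The model-based standard error of the 24-week contrast depends on this, because the fit pools all three visits to estimate one variance and one correlation and then applies them to the baseline–24-week pair. If that pair differs from the pooled pattern, the reported standard error, confidence interval and P value are off.

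Table 1 suggests how this could happen. If the composite is built from whichever tests are available at a visit, the 12-week score rests on fewer tests. It is then noisier and less correlated with the other two visits.

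At stake is the validity of the primary P value, in either direction: excess false positives, or lost power in a 90-person trial. Section 5.3 adds to this. Likelihood-based handling of data missing at random relies on an adequate covariance, and up to 20% dropout is planned for in section 2.3.

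**Working it through.** **Inputs.** From the SAP: three visits; 45 per arm (section 2.3); two-sided 5% (section 3.1); a random intercept as the only random term; five of nine tests at 12 weeks (Table 1). The SAP gives no visit SD or between-visit correlation, so it has no figure to reproduce and every covariance below is an assumption.

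**Formulas (large sample, complete data, common baseline mean).** Let s0 and s24 be the true SDs at baseline and 24 weeks, and c the true 0–24 covariance. Let v be the mean of the three visit variances, and ρ the mean of the three covariances divided by v. The compound-symmetry fit converges to v and ρ. The 24-week effect is then the 24-week arm difference minus ρ times the baseline arm difference.

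- Reported SE² = (2/45) · v(1 − ρ²)
- True SE² = (2/45) · (s24² − 2ρc + ρ²s0²)
- True error rate = 2[1 − Φ(1.96 × reported SE / true SE)]
- Unstructured SE² = (2/45) · s24²(1 − r²), where r is the 0–24 correlation

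**One case in full.** Correlations .80/.80/.64 (0–12, 12–24, 0–24), all SDs 1:

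- ρ = (.80 + .80 + .64)/3 = .7467, so ρ² = .5575.
- Reported SE = √(.04444 × .4425) = 0.140.
- True SE = √(.04444 × (1 − 2 × .7467 × .64 + .5575)) = √(.04444 × .6018) = 0.164.
- Ratio 0.857, error rate 9.3%.

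**Three-visit results.**

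| Correlations 0–12 / 12–24 / 0–24 | Reported SE | True SE | Error rate |
|---|---|---|---|
| .70/.70/.70 (compound symmetry) | 0.151 | 0.151 | 5.0% |
| .72/.72/.68 | 0.149 | 0.155 | 5.9% |
| .75/.75/.65 | 0.147 | 0.161 | 7.3% |
| .80/.80/.64 | 0.140 | 0.164 | 9.3% |
| .80/.80/.64, 24-week SD 1.2 | 0.153 | 0.195 | 12.3% |
| .60/.60/.75 | 0.160 | 0.141 | 2.6% |

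With equal SDs the test is liberal when the 0–24 correlation is below the average of the three, and conservative when it is above.

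**The Table 1 mechanism.** Take the composite as the mean of 9, 5 and 9 tests, with inter-test correlation q, factor correlation f between visits and test-specific stability t. The variance is q + (1 − q)/m for m tests. The covariance is fq + t(1 − q)/9 for every visit pair. For q = .4, f = .85, t = .35:

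- Variances are .467, .520, .467 and every covariance is .363.
- Correlations are .738/.738/.779.
- The SE ratio is 1.07 (error rate 3.6%) on the raw score, and 1.05 (3.9%) if restandardised at each visit.

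Over q .3 to .5, f .8 to .9 and t 0 to .7, the ratio runs from 1.03 to 1.16 and the error rate from 4.4% down to 2.3%.

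**Two-visit outcomes.** There is only one correlation, so only equal variance is imposed. With k the 24-week SD divided by the baseline SD, the SE ratio is √[(1 + k²)/(2k²)], whatever the correlation. For k = 0.9, 1.1 and 1.2 it is 1.057, 0.956 and 0.920, giving 3.8%, 6.1% and 7.1%. For k = 1 it is 5.0%.

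**Simulation with REML.** There were 1,000 runs for each of five covariances, with complete data or 20% missing completely at random at 24 weeks (Monte Carlo SE about 0.7 points).

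| Analysis | Rejection range | Compound symmetry true, complete data |
|---|---|---|
| Random intercept, model SE | 2.5% to 14.0% | 6.0% |
| Unstructured | 4.0% to 6.8% | 5.2% |
| Random intercept, small-sample robust SE | 3.9% to 6.2% | 5.4% |

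**The case against.** The best counter-argument is that the only mechanism found in the document points to a conservative test. Table 1 gives 2.3% to 4.4%. The inflated figures need the adjacent-visit correlations to exceed the 0–24 correlation, or a larger SD at 24 weeks, and the SAP supports neither. That stands: those scenarios show sensitivity and predict nothing. The Table 1 mechanism is also conditional. Section 5.1 chooses the factor model on fit and does not say the composite uses whatever tests are available at each visit. If only tests given at all three visits are retained, that particular reason goes. A conservative primary test is still a fault in a trial of 90.

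Second, the residual structure is unstated, not stated wrongly. Assumptions are to be checked, transformation is only an example remedy, and section 5.3 will revisit the missing-data assumption. These points soften the concern, but none fixes a covariance in advance. A transformation does not generally repair a wrong correlation pattern, and a list of packages selects no model.

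Third, with complete data the estimate itself hardly suffers. The true SE under the random intercept is close to the unstructured SE: 0.164 against 0.162 for .80/.80/.64, and 0.141 against 0.139 for .60/.60/.75. That is right. The problem is the reported SE, and a robust SE alone would repair most of it.

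Fourth, bias under outcome-dependent missingness was not simulated, and a robust-SE fallback would not cure it. That also stands, so the missing-data point is a matter of principle here, without a size. Finally, the unstructured model reached 6.8% in one setting, so it is not exactly nominal. Its range is still far narrower than that of the random intercept.

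**Conclusion.** The concern holds. On the ordinary reading of sections 5.2 and 5.2.1, the primary inference assumes equal variances and a single correlation over three visits, which the SAP neither justifies nor protects against. If compound symmetry is true, nothing is wrong. Otherwise the true error rate at nominal 5% was 2.3% to 4.4% for a composite of nine, five and nine tests, and from 2.6% to 12.3% over the other patterns tried. These figures assume 45 per arm, no true effect, large-sample theory and covariances that the SAP does not supply, so neither direction nor size can be asserted for this trial. For two-visit outcomes only the equal-variance assumption is in question. This should be corrected before the analysis. Confidence is medium, because the true covariance is unknown and the residual structure is left unstated.

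**What to change.** In sections 5.2 and 5.2.1, replace the random intercept with an unstructured within-participant covariance (3×3 for three-visit outcomes, 2×2 for two-visit outcomes), fitted by REML with a named small-sample degrees-of-freedom method. Keep the baseline constraint, and name the 24-week between-group contrast as the test, which section 5.2.1 already targets. State the fallback: if the model does not converge, keep the random intercept and use sandwich standard errors with a small-sample correction. The fallback repairs the standard error but not any bias from a wrong covariance when data are missing at random.

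The cost is one sentence in each section. Three-visit outcomes need 6 covariance parameters instead of 2, and two-visit outcomes 3 instead of 2, with 90 participants. If compound symmetry is true at correlation .7, the large-sample SE is 0.151 either way. LMMstar and nlme, both already listed in section 5.6, can fit the model.
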